7.12.2. Secondary Endpoints Analysis for Extension Study

Week 48 absolute change and percent change from baseline for each Pegozafermin individual dose level group, and for group who re-randomized to Pegozafermin 30mg in the Extension Study will be compared to “Placebo Only Pooled” group using the MMRM method with treatment group, week, and treatment-by-week interactions as main effects, baseline measurement and two stratification factors (T2DM status (yes vs. no) and fibrosis stage (F2 vs. F3)) as covariates in the model. The following clinical parameters will be analyzed:

- Hepatic fat fraction by MRI-PDFF
- ALT
- Pro-C3

An unstructured covariance matrix will be used to represent the correlation of the repeated measures within each subject whenever the model converges.

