A Data Monitoring Committee (DMC) will periodically convene to review unblinded overall safety results per DMC charter (Section 9.8).

Main Study

After signing informed consent, subjects will undergo screening assessments to determine eligibility over a period of 12 weeks. Eligibility period may be extended with Sponsor's approval. Individual screening assessments may be done remotely as part of tiered screening. Subjects will either undergo a liver biopsy during Screening or have a recent liver biopsy (within 6 months prior to consent, available to be evaluated for eligibility by the central reader) that meets study inclusion criteria; ideally, the liver biopsy should be done after all non-invasive eligibility criteria are met.

On Day 1 (baseline), eligible subjects will be randomized to one of the following treatment groups:

- Placebo, N=64; QW (N=42) or Q2W (N=22)
- Pegozafermin 15 mg, QW subcutaneous (SC), N=16
- Pegozafermin 30 mg, QW, SC, N=64
- Pegozafermin 44 mg, Q2W, SC, N=40

with the randomization 16:8:6:24:15 to Placebo QW, Placebo Q2W, pegozafermin 15 mg QW, 30 mg QW and 44 mg Q2W, respectively. The randomization will be stratified by T2DM status (yes vs. no) and fibrosis stage (F2 vs. F3). For the purposes of stratification, subjects will be considered to be T2DM status positive if any of the following criteria are met: current medical history of T2DM, current use of anti-glycemic medication(s) for T2DM, or screening laboratory values HbA1c $\geq 6.5\%$ or fasting plasma glucose ≥ 126 mg/dL. Subjects will receive IP over 24 weeks (includes 24 administrations in QW dose regimen and 12 administrations in Q2W dose regimen). Subjects, investigators and site staff and Sponsor will be blinded to IP (placebo or pegozafermin); however, the dose regimen (QW or Q2W) will be known to all parties involved in the study.

Subjects will undergo a second liver biopsy at the Week 24 visit (window of -7 days to +14 days). Liver biopsies will be read centrally by liver pathologists who are blinded to the treatment group assignment (refer to Section [6.4.3](#) for details).

Extension Study

Subjects completing the Main study will continue for an additional 24 weeks in the Extension study. The Extension study will commence at Main study Week 24 visit.

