At Week 24, subjects randomized to placebo QW in the Main study will be re-randomized 1:1 to pegozafermin 30 mg QW (n=21) or placebo QW (n=21) and receive the re-randomized treatment at the Week 26 visit (which may be an in-clinic or a remote home visit). All other subjects will continue to receive the same treatment regimen in the Extension study that they received during the Main study. IP will be administered over 24 additional weeks (includes 24 administrations in QW dose regimen and 12 administrations in Q2W dose regimen), for approximately 48 weeks of treatment over the entirety of the study (Main and Extension). Specifically-identified Sponsor personnel will not be blinded; however, subjects, investigators and site staff will remain blinded to IP (placebo or pegozafermin). Dose regimen (QW or Q2W) will be known to all parties in the Extension study.

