The primary endpoints of the Main study will further assess the effect of different doses/regimens of pegozafermin on improvement in liver histological endpoints compared to baseline at Week 24, including, 1) NASH resolution without worsening of fibrosis and \geq 2-point improvement in NAS score, 2) improvement of fibrosis \geq 1 stage without worsening of NASH and \geq 2-point improvement in NAS score. These modified histological primary endpoints are consistent with the FDA guidance on endpoints likely to predict clinical benefit and incorporate NAS improvement as a measure that reflects decrease in disease severity, thus is clinically meaningful ([Neuschwander-Tetri, 2015](#); [Harrison, 2019](#); [FDA Draft Guidance for Industry, December 2018](#)). Other Main study secondary efficacy endpoints include changes in liver fat, other histological endpoints, and additional liver and metabolic biomarkers. The study will contribute to further characterization of the safety profile for pegozafermin. Patient reported outcomes and other exploratory endpoints will also be assessed. Efficacy data from this study, in particular findings related to the effect of pegozafermin at the studied doses and dose regimens on the assessed histological endpoints, will support dose selection and endpoint determination in the anticipated Phase 3 program.

The Extension study will allow long-term safety (including long-term immunogenicity) and evaluation of noninvasive biomarker assessments in a single-blinded manner. The re-randomization of subjects assigned to placebo QW treatment arm in Main study to receive either active (pegozafermin 30 mg QW) or placebo QW will allow replication of the pegozafermin effects on noninvasive biomarker results observed in the Main study. The two-week delay in treatment change for this group will ensure that all biopsies are performed prior to any of these subjects being switched from placebo to IP.

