7. STATISTICAL METHODS OF ANALYSES

7.1. General Considerations

The primary analysis will include data up to the min of (28 days after the last dose date before the completion of all Week 24 assessments, the date all Week 24 assessments completed, Main Study cut-off date).

At final analysis, safety summaries including extent of exposure will report data from both Main Study and Extension Study, based on safety analysis set.

Continuous variables will be summarized by number of patients, mean, standard deviation (SD)/ standard error (SE), median, minimum, and maximum values. Minimum and maximum will be presented to the same number of decimal places as reported/collected. One additional decimal place will be presented for mean and median. Two additional decimal places will be presented for SD/ SE up to a max of three decimal places.

Categorical variables will be summarized by number and percentage of patients. Percentage will be presented to one decimal place. The number of missing values will be presented as a separate category with no percentage, but only if 1 or more patients are missing data for the summary. Otherwise, all categories will be presented (even if no patients are counted in the category). Counts of zero in any category will be presented without percentage.

For analysis purpose, placebo QW and placebo Q2W will be pooled except for exposure summaries and pre-specified supportive analyses.

All statistical tests will be 2-sided and tested at a statistically significant level of 0.05 without adjustment for multiplicity. Confidence intervals will be 2-sided 95%, unless stated otherwise. Two-sided p-values will be presented with four decimal places and values less than 0.0001 will be presented as <.0001.

Both reported units (CN) and standard units (SI) will be presented in listings. Only CN units will be used for tables and figures, unless otherwise specified. Insulin will be presented with conventional unit of μ IU/mL.

All applicable analyses for the primary analysis of the Main Study will be presented as:

<Description>	Placebo Pooled	Pegozafermin 15 mg QW	Pegozafermin 30 mg QW	Pegozafermin 44 mg Q2W
---------------	-------------------	--------------------------	--------------------------	---------------------------

A total column will be presented for the disposition, demography, protocol deviation, medical history, prior/concomitant medication/procedure, and other subject information summaries.

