7.12. Final Analysis

All safety and efficacy tables in final analysis will be presented as:-

Description	Placebo Only Pooled	Pegozafermin 15 mg QW	Pegozafermin 30 mg QW Only	Pegozafermin 44 mg Q2W	Placebo (main) and Pegozafermin 30 mg QW (Extension)
-------------	------------------------	--------------------------	----------------------------------	---------------------------	---

Groups “Placebo Only Pooled” and “Pegozafermin 30 mg QW Only” contain subjects who received the same treatment during the Main Study and the Extension Study. Group “Placebo (main) and Pegozafermin 30 mg QW (Extension)” contains subjects who switched to Pegozafermin 30 mg QW treatment in the Extension Study.

Safety summaries for final analysis will be presented by the actual treatment subject received based on the Safety Analysis Set except for subjects who re-randomized to Pegozafermin 30mg treatment group in the Extension Study. Subjects who switched the treatment group at Extension Study will be summarized under “Placebo (main) and Pegozafermin 30 mg QW (Extension)” group.

Final Efficacy analysis (secondary endpoints of Extension Study) will be performed based on the Full Analysis Set with confirmed fibrosis stage F2 or F3 and NAS ≥ 4 at baseline per 3- panel consensus read and by the randomized treatment group in Main Study.

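### SAP 7.12.2 never specifies the comparison that the Extension re-randomisation protects: subjects switched to 30 mg QW against subjects re-randomised to placebo QW

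*SAP*

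**What the plan says.** **Purpose.** Protocol 4.2 explains that the re-randomisation "will allow replication of the pegozafermin effects on noninvasive biomarker results observed in the Main study".

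**Who is re-randomised.** Under Protocol 4.1, only the 42 placebo QW subjects are re-randomised, 1:1, with 21 planned per group. The new treatment starts at Week 26. The 22 placebo Q2W subjects are not re-randomised: "All other subjects will continue to receive the same treatment regimen in the Extension study that they received during the Main study".

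**Comparator.** SAP 7.12 says that the Placebo Only Pooled and 30 mg QW Only groups "contain subjects who received the same treatment during the Main Study and the Extension Study". SAP 7.1 says that "placebo QW and placebo Q2W will be pooled except for exposure summaries and pre-specified supportive analyses". The pool is therefore placebo Q2W plus the placebo QW subjects re-randomised to placebo.

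**Planned contrast.** In SAP 7.12.2, Week 48 absolute and percent change in MRI-PDFF, ALT and Pro-C3 for each dose level "and for group who re-randomized to Pegozafermin 30mg in the Extension Study will be compared to" the Placebo Only Pooled group. The method is an MMRM with the baseline measurement, T2DM status and fibrosis stage as covariates.

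**Baseline.** SAP 5.1 sets it at or before the first dose of study drug (for ALT, an average of screening and Day 1 values). No Week 24 baseline is defined.

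**Grouping.** SAP 7.12 also says that final efficacy is analysed in the FAS and "by the randomized treatment group in Main Study". SAP 5.2, the column layout in SAP 7.12 and SAP 7.12.2 all give switchers a group of their own.

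**The concern.** The second randomisation protects one contrast: among placebo QW subjects who reached Week 24, those assigned to 30 mg QW against those assigned to stay on placebo QW. Nothing in SAP 7.12 asks for it. The only comparison planned for the switchers adds placebo Q2W subjects to the control side, and the model has no term for placebo regimen.

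Two further features weaken it as a replication. The change is measured from Day 1, so for switchers it is mostly time on placebo. And the treatment-by-week MMRM gives each group its own Week 24 mean, so a chance difference at the point of re-randomisation is carried into the Week 48 estimate. No stratification is stated for the re-randomisation (Protocol 6.4.1, SAP 3.3), and the groups are small.

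At stake is whether the trial reports the replication that its design paid for with a second randomisation.

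**Working it through.** **1. The plan's own figures.** Neither document gives a power or precision for the Extension contrast. The placebo sizes follow from the allocation ratio: 184 × 16/69 = 42.7 and 184 × 8/69 = 21.3, against 42 and 22 stated. The Main Study powers in SAP 3.5 reproduce with a pooled-variance test of two proportions, two-sided 0.05, and sizes cut by 15%. With 54.4 v 54.4 the result is 93.8% and 91.8% (stated 94% and 92%); with 34 v 54.4 it is 87.1% and 84.0% (stated 87% and 83%). So 15% is used below as the planning dropout.

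**2. Share of the pool never re-randomised.** 22 / (22 + 21) = 22/43 = 51.2%. QW:Q2W placebo is 2:1 under both the initial 2:1:3:3:3 ratio and the later 16:8:6:24:15 ratio (SAP 3.3), so a 1:1 split of QW gives 1/(1 + 1) = 50% by ratio alone.

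**3. Effect of early dropouts** (equal dropout in both placebo arms assumed). If only Week 24 completers count, then at 15% dropout: 22 × 0.85 = 18.7 Q2W and 42 × 0.85 / 2 = 17.85 QW, so 18.7/36.55 = 51.2% again. If placebo subjects who stop before Week 24 are kept in the pool, the share is (22 + 42d) / (22 + 42d + 21(1 − d)):

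| Dropout d | Share never re-randomised |
|---|---|
| 5% | 24.1/44.05 = 54.7% |
| 10% | 26.2/45.1 = 58.1% |
| 15% | 28.3/46.15 = 61.3% |

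**4. Size of any bias from regimen.** If placebo Q2W and placebo QW differ by δ, the pooled mean moves by (22/43)δ = 0.51δ. For an assumed δ of 0.25 SD that is 0.13 SD. If δ is zero there is no such bias.

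**5. Precision** (common SD, no covariates, planned sizes; detectable difference = (1.960 + 0.842) × SE).

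| Contrast | SE in SD units | Detectable at 80% power |
|---|---|---|
| Planned, 21 v 43 | √(1/21 + 1/43) = 0.266 | 0.75 SD |
| Re-randomised only, 21 v 21 | √(2/21) = 0.309 | 0.86 SD |

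The ratio is 0.309/0.266 = 1.16. At 15% dropout the SEs are 0.289 and 0.335, with the same ratio.

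**6. Week 24 adjustment.** The SE ratio becomes 1.16 × √[(1 − r₂₄²)/(1 − r₀²)], where r₂₄ is the correlation of Week 24 with Week 48 and r₀ that of baseline with Week 48. The documents give neither. Assuming r₀ of 0.3 to 0.7, r₂₄ of 0.5 to 0.8, and r₂₄ no smaller than r₀, the ratio runs from 0.73 (r₀ = 0.3, r₂₄ = 0.8) to 1.16 (the two equal).

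**7. Time on each treatment.** For switchers, Day 1 to Week 48 is about 26 weeks of placebo and 48 − 26 = 22 weeks of drug. The Main Study change is over 24 weeks on the assigned treatment.

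**The case against.** Several points on the other side stand.

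- A reader might infer that the pool mixes randomised with non-randomised controls. It does not. Placebo Q2W subjects were randomised on Day 1 in the same stratified scheme, run concurrently and are blinded to drug or placebo. MRI-PDFF is read by a central vendor and the laboratory tests are central, so knowing the regimen is a weak route to a difference in these endpoints.
- A reader might infer that the Day 1 baseline biases the Week 48 difference. It does not: switchers and placebo controls share the same pre-switch placebo period. Change from baseline at Week 48 is also the endpoint in Protocol 3.2, so the SAP follows the protocol.
- A reader might infer that the replication question goes unanswered. That is too strong. Protocol 4.2 is design rationale, the listed objective is to characterise the effect, and switchers are compared with placebo, with the same pooling and baseline as the Main Study.
- A literal reading of SAP 7.12 keeps pre-Week 24 dropouts out of the pool, because they received nothing in the Extension. But the final efficacy population is the FAS, which includes them, and the layout has no other placebo column.
- Protocol 9.4 plans supportive analyses of each QW arm against placebo QW without limiting them to the Main Study. SAP 7.8.1 places them under Main Study efficacy and SAP 7.12 does not carry them over. Even if carried over, they do not say how to treat a placebo QW arm that has been split.
- The sentence on Main Study randomised group is probably a slip, since the same section gives switchers a separate column. It still conflicts with the text around it.

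**Conclusion.** The point holds as an omission: the contrast created by the second randomisation is not pre-specified, and the one that is planned uses a comparator of which about 51% was never re-randomised (up to 61% at 15% dropout if early placebo dropouts are retained). The documents do not show that the planned estimate is biased. Bias needs a real difference between placebo regimens or retention of early dropouts. The Day 1 baseline costs adjustment for Week 24 imbalance and makes the switchers' change unsuitable to set beside the Main Study 24-week change.

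The figures rest on planned sizes, equal placebo dropout and a common SD. Actual FAS numbers may be below 21 per group, because the FAS requires stage F2 or F3 and NAS ≥4 on the three-pathologist read. The earlier study's reductions (up to 60% in liver fat, 44% in ALT and 28% in Pro-C3; Protocol 2.3.2) come without SDs, so they cannot be turned into power here.

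These are secondary endpoints, tested without multiplicity adjustment, in an Extension whose primary endpoint is safety. The change is worth making, but nothing in the primary histology analysis depends on it.

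**What to change.** In SAP 7.12.2, before final database lock:

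1. Add a pre-specified replication analysis: re-randomised 30 mg QW against re-randomised placebo QW, among FAS subjects who were re-randomised, at Week 48. Covariates are the Week 24 value, T2DM status and fibrosis stage. Use ANCOVA for MRI-PDFF and MMRM over the post-Week 24 visits for ALT and Pro-C3.
2. Keep the pooled comparison of change from baseline, which matches the protocol endpoint.
3. State that the pool is limited to subjects who entered the Extension when it is compared with switchers.
4. In SAP 7.12, reword the sentence on Main Study randomised group so that switchers stay in their own group, consistent with SAP 5.2, 7.12.2 and the column layout.

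The cost is one extra model per parameter and no new data, since all three parameters are already Main Study endpoints at Week 24. The interval will be wider than the pooled one by a factor of up to about 1.16, which Week 24 adjustment may offset. The new contrast will still reflect about 22 weeks of drug rather than 24, and the report should say so.

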7.12.3. Safety, PK, and Exploratory Endpoints for Extension Study

Change from baseline and percentage change from baseline at each post baseline scheduled visits for all safety and exploratory endpoints listed in Section 4.2.3 and Section 4.2.4 will be summarized at final analysis based on safety analysis set, following the same layout as the primary analysis but extend to the pooled data of both Main Study and Extension Study.

The proportion of patients with ≥ 17 U/L decrease in ALT at each visit of Main Study and Extension Study will be summarized.

PK analysis will be repeated in final analysis including PK data from both Main Study and Extension Study. Completed Immunogenicity data including data collected during the immunogenicity follow-up period will be analyzed separately.

REFERENCE

Akero Therapeutics Inc. (2020). "Press Release: Akero Announces Strongly Positive Histological Data Across All Efruxifermin Dose Groups in 16-Week Phase 2a BALANCED Study in NASH Patients." from <https://ir.akerotx.com/news-releases/news-release-details/akero-announces-strongly-positive-histological-data-across-all>.

Drenth, J. P. H. and Schattenberg, J. M. (2020). "The nonalcoholic steatohepatitis (NASH) drug development graveyard: established hurdles and planning for future success." *Expert Opinion on Investigational Drugs* 29(12): 1365-1375.

Han, M. A. T., Altayar, O., Hamdeh, S., Takyar, V., Rotman, Y., Etzion, O., et al. (2019). "Rates of and Factors Associated With Placebo Response in Trials of Pharmacotherapies for Nonalcoholic Steatohepatitis: Systematic Review and Meta-analysis." *Clin Gastroenterol Hepatol* 17(4): 616-629.e626

Harrison, S. A., Neff, G., Guy, C. D., Bashir, M., Gunn, N. T., Paredes, A. H., et al. (2020a). Positive topline results from a 24-week, randomized, double-blind, placebo-controlled, multicenter, phase 2 study of the FGF19 analogue aldafermin (NGM282) in patients with nonalcoholic steatohepatitis. European Association for the Study of the Liver/The Digital International Liver Congress 2020, London, UK.

Harrison, S. A., Rossi, S. J., Paredes, A. H., Trotter, J. F., Bashir, M. R., Guy, C. D., et al. (2020b). "NGM282 Improves Liver Fibrosis and Histology in 12 Weeks in Patients With Nonalcoholic Steatohepatitis." *Hepatology* 71(4): 1198-1212.

APPENDIX 1. SCHEDULE OF ACTIVITIES (SOA)

Subjects will attend clinic visits for Screening, Baseline (Day 1), Week 4, Week 12, Week 24, Week 38 and Week 48/ET. Note the sections referred in the table correspond to the sections in the protocol.

Assessments	Screening Period ¹	Treatment Period										FU Period	Notes:
		Main Study					Extension Study						
Study Day		1 ²											
Study Weeks	-12 to 0		4 ³	8 ⁴	12 ³	16 ⁴	24 ³	26 ⁵	30 ⁴	38 ³	48 ³	ET ^{3,6}	51 ⁷ /EOS
Visit window (days)			±2	±7	±7	±7	±7	+7	±7	±14	+14		±14
Informed consent	X												
Medical history/ demographics	X												
Liver biopsy	X ^a					X ^b				X ^c		Liver biopsies should ideally be done after MRI-PDFF. a. Must meet study inclusion criteria. A biopsy performed within 6 months of screening is acceptable instead of the baseline liver biopsy if the sample is deemed interpretable and eligible by the central reader. b. To be performed at -7 to +14 days of the Week 24 target visit; if biopsy not performed by Week 26 for subjects in QW groups, W26 dose to be held until discussion with Sponsor c. Applicable for subjects who discontinue IP at or after Week 16 and before Week 24 of the Main Study.	
Histology machine read (PathAI)	X				X				X ^c				c. Applicable for subjects who discontinue IP at or after Week 16 and before Week 24 of the Main Study.
Prior medications	X												
Inclusion and exclusion criteria	X	B											

Assessments	Screening Period ¹	Treatment Period										FU Period	Notes:
		Main Study					Extension Study						
Study Day		1 ²											
Study Weeks	-12 to 0		4 ³	8 ⁴	12 ³	16 ⁴	24 ³	26 ⁵	30 ⁴	38 ³	48 ³	ET ^{3,6}	51 ⁷ /EOS
Visit window (days)			±2	±7	±7	±7	±7	+7	±7	±14	+14		±14
Complete physical exam	X ^d					X			X				d. includes recording height, weight, and calculating BMI.
Limited physical assessment ^e		B	X	X	X	X		X	X		X		e. if clinically indicated. May be performed by home health nurse for remote visits.
Body weight	X	B		X		X			X	X	X		The Investigator will be requested to further evaluate subjects with weight loss of ≥15.0% at Week 12 and ≥20.0% at Week 24, from baseline, for the potential cause of weight loss.
Waist and hip circumferenc	X	X		X		X			X	X	X		
Lifestyle counseling	X	X	X	X	X	X		X	X				Strenuous exercises should be avoided for at least 48 hours prior to study visits.
Fibroscan VTCE and CAP	X ^f					X			X	X			f. Fibroscan should ideally be performed prior to MRI-PDFF. At Screening, a historical Fibroscan assessment performed within the last 3 months prior to screening may be acceptable.
12-lead ECG (single) ^g	X	B		X		X			X	X	X		g. ECGs will be recorded as single bedside measurements. Additional ECG may be conducted if clinically indicated. ECG should be performed prior to vital signs and laboratory assessments. All ECG data should be provided within 72 hours to the central reader for assessment.
Urine drug screen	X ^h												h. Urine drug screen will be done locally with a standardized kit during screening period by Day 1. If cannot be performed during screening, test can be performed on Day 1, but must be completed before randomization procedures start. Refer to Appendix 2 (Section 10.2).

Assessments	Screening Period ¹	Treatment Period										FU Period	Notes:
		Main Study					Extension Study						
Study Day		1 ²											
Study Weeks	-12 to 0		4 ³	8 ⁴	12 ³	16 ⁴	24 ³	26 ⁵	30 ⁴	38 ³	48 ³	ET ^{3,6}	51 ⁷ /EOS
Visit window (days)			±2	±7	±7	±7	±7	+7	±7	±14	+14		±14
Hematology, and coagulation	X	B	X		X		X	X	X	X	X		Refer to Appendix 2 (Section 10.2) for laboratory parameters.
Biochemistry	X ⁱ	B	X	X	X	X		X	X	X	X		Refer to Appendix 2 (Section 10.2) for laboratory parameters. i. For all subjects, ALT and AST will be collected twice during the Screening period at least 2 weeks apart between the 1 st and 2 nd assessment. A 3 rd assessment, if required, will be collected via unscheduled visit, and performed at least 1 week apart from the 2 nd assessment (refer to Exclusion criterion in Section 5.2.)
FSH	X												Only if required to confirm menopausal status in women under the age of 45 who have amenorrhea >12 months and are not using hormonal contraception or hormone replacement therapy.
LH, FSH, Estradiol		X				X			X				Only for WOCBP who are not on hormonal contraception.
Urinalysis	X	B	X		X	X		X	X	X			
HbA1c	X	B		X	X			X	X	X			
HOMA-IR	X	B		X	X			X	X	X			
IGF-1		B		X	X			X	X	X			
Serology	X												Refer to Appendix 2 (Section 10.2) for laboratory parameters (HBsAg, HCV and HIV 1 and 2 antibodies [HCV RNA reflex for HCV Ab+ only]).
Thyroid panel (TSH, FT4, TT3)	X			X	X			X	X	X			

Assessments	Screening Period ¹	Treatment Period										FU Period	Notes:
		Main Study					Extension Study						
Study Day		1 ²											
Study Weeks	-12 to 0		4 ³	8 ⁴	12 ³	16 ⁴	24 ³	26 ⁵	30 ⁴	38 ³	48 ³	ET ^{3,6}	51 ⁷ /EOS
Visit window (days)			±2	±7	±7	±7	±7	+7	±7	±14	+14		±14
Pregnancy test in WOCBP only ^j	X (Serum)	B	X	X	X	X	X		X	X	X	X	j. Serum pregnancy test will be conducted at Screening; at all other timepoints urine pregnancy test will be done. For in-clinic visits at the indicated timepoints, a urine pregnancy test will be obtained locally. If the urine test is positive, dosing should be withheld, a confirmatory serum pregnancy test should be sent to the central laboratory, and the Sponsor should be notified.
Vital signs ^k (blood pressure, pulse, body temperature, and respiratory rate)	X	B	X	X	X	X	X		X	X	X	X	k. Vital signs will be measured prior to scheduled blood draws. Starting from randomization, blood pressure and pulse will be measured in duplicate, the first measurement will be taken up to 15 minutes before the indicated timepoint. Additional vital signs measurement may be done if clinically indicated. Subjects must be in a supine or semi-erect/seated position and resting for at least 5 minutes prior to measurements. Repeat measurements should be performed according to local practice.
Patient reported		B		B	B				X	X			
Randomization		X					X ^l						l. for Extension Study (Placebo QW) At Week 24, subjects randomized to placebo QW in the Main Study will be re-randomized 1:1 to pegozafermin 30 mg QW (n=21) or placebo QW (n=21).

Assessments	Screening Period ¹	Treatment Period										FU Period	Notes:	
		Main Study					Extension Study							
Study Day		1 ²												
Study Weeks	-12 to 0		4 ³	8 ⁴	12 ³	16 ⁴	24 ³	26 ⁵	30 ⁴	38 ³	48 ³	ET ^{3,6}	51 ⁷ /EOS	
Visit window (days)			±2	±7	±7	±7	±7	+7	±7	±14	+14		±14	
Dispense IP		X	<=====X ^m =====>										m. Sponsor-approved courier services may provide IP to subjects from Week 4 through EOS. Depending on geography this may be direct-to-subject shipment or may require site to-subject shipment. Instructions for dispensation and IP shipment to site and direct-to-subject shipment will be detailed in the Pharmacy Manual. IP should be dispensed approximately every 4 weeks.	
IP administration ⁿ		X	QW from Weeks 1 to 23		QW from Weeks 24 ^o to 47								Dosing window is ±2 days, however for QW dosing, every effort should be made to take IP on the same day of the week and must be at least 5 days between 2 doses.	
			Q2W from Weeks 2 to 22		Q2W from Weeks 24 to 46								n. IP will be administered SC to the abdomen by trained and qualified study personnel, site staff at clinic visit(s), or at home by healthcare professional, or subject's caregiver for home administration. IP may also be self-administered at the subject's home.	
													o. Week 26 may be an in-clinic or a remote/home visit by healthcare professional who will administer the IP.	
PK blood collection ^p		B	B	B	B		B			B	X	X		p. PK blood samples will be collected predose. Additional blood samples for PK analysis may be collected if clinically indicated (e.g., in case of SAE). For PK sample collection instruction/procedures, refer to the relevant manual.

Assessments	Screening Period ¹	Treatment Period										FU Period	Notes:
		Main Study					Extension Study						
Study Day		1 ²											
Study Weeks	-12 to 0		4 ³	8 ⁴	12 ³	16 ⁴	24 ³	26 ⁵	30 ⁴	38 ³	48 ³	ET ^{3,6}	51 ⁷ /EOS
Visit window (days)			±2	±7	±7	±7	±7	+7	±7	±14	+14		±14
ELF panel, Pro-C3, adiponectin, FIB-4 index (derived calculation), and adipo-IR (fasting free fatty acids x fasting insulin)		B		X		X			X	X	X		Refer to Appendix 2 (Section 10.2).
Night-time salivary cortisol (NSC) ^q	X ^q			X	X			X	X	X			q. NSC sample will be collected by subject at home between 8:00pm and 12:00am before submitting the sample for processing at the specified visit. If the sample is not collected between 8:00pm and 12:00am, the test should be repeated. The screening assessment should be performed as early as possible during the screening period. Subjects should be provided with NSC collection kit at the first screening visit, when possible, to allow sample collection return at the following clinic visit. If screening value is >15 nmol/L, Medical Monitor (or designee) may request further workup should the value be of clinical concern; however, values >15 nmol/L will not be exclusionary. The screening NSC is a safety assessment, and not an I/E criteria. Refer to Section 10.2 for further requirement for Value >15 nmol/L on treatme

Assessments	Screening Period ¹	Treatment Period										FU Period	Notes:
		Main Study					Extension Study						
Study Day		1 ²											
Study Weeks	-12 to 0		4 ³	8 ⁴	12 ³	16 ⁴	24 ³	26 ⁵	30 ⁴	38 ³	48 ³	ET ^{3,6}	51 ⁷ /EOS
Visit window (days)			±2	±7	±7	±7	±7	+7	±7	±14	+14		±14
MRI-PDFF	X			X	X				X	X			
At Screening, MRI-PDFF should ideally be done before liver biopsy. At Screening, a historical MRI-PDFF assessment performed within the last 3 months prior to screening may be acceptable if the images are available and evaluable by the central imaging vendor.
 
On treatment, MRI-PDFF should ideally be done within ± 7 days of the target visit date. If out of the window, MRI-PDFF should be performed as close to the target visit date.

cT1	X			X	X				X	X			
Iron-corrected T1 mapping.
 
Applicable only at sites capable of conducting cT1 imaging.
 
At Screening, a historical cT1 assessment performed within the last 3 months prior to screening may be acceptable if the images are available and evaluable by the central imaging vendor.

Liver/Spleen volume and pancreatic fat	X			X	X				X	X			
To be done at the same time as MRI-PDFF.
 
At Screening, a historical liver/spleen volume and pancreatic fat assessment performed within the last 3 months prior to screening may be acceptable if the images are available and evaluable by the central imaging vendor.

Bone Mineral Density (BMD) by Dual X Ray Absorptiometry (DXA) ^r		X			X				X	X			
DXA should be done within -14/+7 days of the target visit date. If out of the window, DXA should be performed as close to the target day as possible.

Plasma for bone biomarkers		B		X	X				X	X			Includes CTX, P1NP, and osteocalcin; refer to Appendix 2 (Section 10.2).

Assessments	Screening Period ¹	Treatment Period										FU Period		Notes:
		Main Study					Extension Study							
Study Day		1 ²												
Study Weeks	-12 to 0		4 ³	8 ⁴	12 ³	16 ⁴	24 ³	26 ⁵	30 ⁴	38 ³	48 ³	ET ^{3,6}	51 ⁷ /EOS	
Visit window (days)			±2	±7	±7	±7	±7	+7	±7	±14	±14		±14	
Endogenous FGF21 ^s		B												s. Baseline samples of endogenous FGF21 will be obtained in all subjects; additional samples will be obtained at the immunogenicity follow-up visits (See the SOA for immunogenicity follow-up period). Endogenous FGF21 samples (baseline and follow-up visit) will be analyzed only in
Immunogenicity		B	X	X	X	X	X		X	X ^t	X			See the SOA for immunogenicity follow-up.
Pharmacogenomic (DNA) blood sampling		X												Optional.
Blood sample for exploratory biomarkers		X					X			X	X			
Adverse event monitoring ^u	X	X	<=====X=====>						X	X				u. The sites may take non-personally identifying photographs of potential injection site reactions (optional).
Concomitant	X	X	<=====X=====>						X	X				

Abbreviations: ALT, alanine aminotransferase; AST, aspartate aminotransferase; B, predose; CTX, carboxy-terminal collagen crosslinks; D, Day; ECG=electrocardiogram; ELF, enhanced liver fibrosis; EOS, end of study; ET= early termination; FGF21, fibroblast growth factor 21; FIB-4, Fibrosis-4 index; FU, Follow-Up; HbA1c=glycated hemoglobin; HBsAg, hepatitis B surface antigen; HCV, hepatitis C virus; HIV, human immunodeficiency virus; HOMA- IR, homeostatic model assessment for insulin resistance; I/E, inclusion/exclusion; IGF-1, insulin-like growth factor 1; IP, investigational product; LH, luteinizing

hormone; MRI-PDFF, magnetic resonance imaging based proton density fat fraction; NSC, night-time salivary cortisol; P1NP, N-terminal propeptide of type 1 collagen; PK=pharmacokinetic; Pro-C3, N-terminal propeptide of type III collagen; QW, once weekly; Q2W, every 2 weeks; S, serum; TSH, thyroid stimulating hormone; WOCBP=women of child-bearing potential

Schedule of Activities (Immunogenicity Follow-up Period)

Assessments	Immunogenicity Follow-up Period				Notes:
	Visit	FU Visit 1	FU Visit 2	FU Visit 3	
Study Week	60	72	84	96	
Visit Window (Days)	± 14	± 14	± 14	± 14	
Immunogenicity ^a	X	X	X	X	
a. Subjects who complete the Week 48 visit will be asked to return to clinic to have blood samples collected approximately every 3 months for up to one year. Additional testing may be requested in the event of safety-related concerns. The sponsor may elect to terminate participation in the immunogenicity follow-up period based on emerging data.

Endogenous FGF21 ^b		X		X	b. Endogenous FGF21 samples will only be analyzed for NAb+ subjects.
Adverse event monitoring ^c	X	X	X	X	c. Immunogenicity testing for a longer follow-up may be requested in the event of safety-related concerns.
Concomitant medications ^d	X	X	X	X	d. Changes and new concomitant medication will be recorded.

Abbreviations: FGF21 = fibroblast growth factor 21; FU = follow-up; Nab+ = Neutralizing antibody positive

